**Risks of Procedures:**

Side effects of dalbavancin include:

Most Common

- Nausea (5.5%)
- Vomiting (2.8%)
- Diarrhea (4.4%)
- Headache (2.7%)
- Rash (2.7%)
- Pruritus (2.1%)

Less Common (Less than 2% of patients)

- Anemia, hemorrhagic anemia, leucopenia, neutropenia, thrombocytopenia, petechiae, eosinophilia, thrombocytosis, gastrointestinal hemorrhage, melena, hematochezia, abdominal pain, infusion-related reactions, hepatotoxicity, anaphylactic reaction, *Clostridium difficile* colitis, oral candidiasis, vulvovaginal mycotic infection, hepatic transaminases increased, blood alkaline phosphatase increased, international normalized

ratio increased, blood lactate dehydrogenase increased, gammaglutamyl transferase increased, hypoglycemia, dizziness, bronchospasm, flushing, phlebitis, wound hemorrhage, spontaneous hematoma

It is not expected that patients will have all of these side effects. Other side effects may occur that were not seen before. Side effects are usually temporary and manageable. However, it is possible that these side effects could be serious or fatal.

#### Risk of development of drug-resistant bacteria

Receiving dalbavancin in the absence of a proven or strongly suspected bacterial infection increases the risk of the development of drug-resistant bacteria. Currently there are no reported cases of dalbavancin resistance reported within the literature. Dalbavancin also shows extremely high potency against medically important *Staphylococcal* and *Streptococcal* species, including methicillin resistant *Staphylococcus aureus*. To date in vitro dalbavancin resistance has not been induced but possible mutations have increased the minimum inhibitory concentration. This has not been seen clinically, and we will maximize the minimum inhibitory concentration to area under the curve ratio, utilizing the 1500 mg dosing strategy.

#### Risk of Blood Draw

During the two long study visits a hollow needle/plastic tube will be placed in each patient's arm for taking blood samples and will be left in arm until the last blood draw. There may be some minor discomfort associated with the needle/plastic tube taped to arm. In about 1 in 10 cases, a small amount of bleeding under the skin will produce a bruise. The risk of a blood clot forming in the vein is about one in 100, while the risk of infection or significant blood loss is one in 1000.

#### **E. Potential Scientific Problems:**

We have given careful consideration to potential obstacles in conducting this study and how we will address them. *Recruitment*. Subjects will be recruited through current clinical relationships through [name] clinical practice at the University of Colorado Hospital. [name] is responsible for the management of a significant number of patients requiring peritoneal dialysis through his clinic. *Retention*. Subject compensation is distributed over the course of the study to encourage continued participation. *Generalizability to peritoneal dialysis patients with peritonitis*. This study must be performed in non-infected volunteers as the dalbavancin pharmacokinetic profile and therapeutic efficacy for the treatment of peritonitis is not currently established. Also it is unclear if the pharmacokinetics of dalbavancin in non-infected volunteers undergoing peritoneal dialysis would be the same as patients undergoing peritoneal dialysis with active peritonitis. The pharmacokinetic profiles between non-infected volunteers and patients with acute bacterial skin and skin structure infections were previously found to be similar.

#### **F. Data Analysis Plan:**

##### *Dalbavancin concentration measurements:*

Dalbavancin concentration analysis will be performed utilizing a LC with MS/MS utilizing a previously published method at the Medicinal Chemistry Core, run by [name], part of the University of Colorado Center for Translational Pharmacokinetics and Pharmacogenomics. The center laboratory is a Clinical Laboratory Improvements Amendments (CLIA) certified laboratory. [name] is a member of this center and will oversee all data processing and analysis.

##### *Pharmacokinetic analysis:*

Plasma and peritoneal fluid concentration-time data for dalbavancin will be evaluated using a multi-compartment model in Phoenix WinNonlin (Pharsight corporation). One, two, and three compartment models will be explored. The following PK parameters will be calculated for plasma and dialysate samples: Cmax – measured, Tmax – measured, Cmin – measured. Fraction of intraperitoneal (IP) dose absorbed [(Dose – drug concentration remaining in dialysate at end of

antibiotic dwell)/Dose].  $K_{el}$  – elimination rate constant.  $T_{1/2} = 0.693/K_{el}$ .  $K_{pc0-6}$  – rate constant for distribution of dalbavancin from peritoneal cavity between 0-6 hours. Distribution half-life in the peritoneal cavity between 0-6 hours ( $t_{1/2} = \ln 2/k_{pc0-6}$ ). Clearance systemic =  $(F \times \text{Dose})/AUC_{0-\infty}$ . Clearance peritoneal – dalbavancin concentration in spent dialysate/AUC of peritoneal fluid. Non-dialysis clearance –  $Cl = Cl_{plasma} - Cl_{peritoneal}$ .  $AUC_{0-\infty}$  – linear trapezoidal method.  $AUC_{0-12}$  hours – linear trapezoidal method. Volume of distribution for each compartment –  $Cl/k_{el}$ ; nonsteady state equations will be utilized. The ratio of plasma dalbavancin to dialysate plasma concentration at each time point –  $C_{plasma}/C_{dialysate}$  and via  $AUC_{plasma}/AUC_{dialysate}$ . Given the sample size of 10 patients completing each treatment modality we will be able to calculate means and standard deviations for all included pharmacokinetic parameters. We will incorporate the dalbavancin PK parameters into a nonlinear mixed effects model (NONMEM) or ADAPT II to determine the pharmacokinetics and examine the effects of varying dosing strategies on plasma and peritoneal fluid concentrations.

*Analysis of pharmacodynamic targets:*

Pharmacodynamic parameters will be evaluated in order to determine whether dalbavancin dosing results in initial and steady-state plasma and peritoneal concentrations that are adequate for treatment of infections due to common pathogens (Staph aureus, Coag neg staph, and enterococcus). Monte Carlo simulation (Crystal Ball version 7, Decisioneering, Inc., Denver, CO) will be used in this study to calculate probability of target attainment (PTA) for pharmacodynamic goals. The model randomly applies values for  $C_{max}$  and  $AUC_{0-12}$  derived from data obtained from the study patients. We will utilize CLSI and EUCAST MIC data for the common gram positive pathogens. We will place these MIC distributions into our Monte Carlo simulation for comparison to dalbavancin plasma concentrations and PK variability. From these studies, MIC frequency distributions will be constructed and used in the Monte Carlo simulations. Ten thousand simulations will be performed at each MIC value and for each of the selected pathogens.

[figure not shown]
[figure not shown]
*Statistical comparisons of PK/PD findings*

Intra-patient pharmacokinetics and pharmacodynamics of dalbavancin will be compared between intravenous and intraperitoneal administration using the paired-t test. Given the sample size of 10 patients completing each phase of the study, we will be able to detect a mean difference in area under the curve between the two treatment modalities of 1527 mg·hr/L at a power of 80%. Probability of target attainment will be compared with the paired t-test. Statistical comparisons will be compared using SAS version 9.3. A p-value < 0.05 will be considered significant.

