### IV. Research Methods

#### A. Outcome Measure(s):

The primary endpoints for the study are to (1) determine dalbavancin plasma pharmacokinetics in peritoneal dialysis patients after intravenous and intraperitoneal administration and (2) determine dalbavancin peritoneal fluid pharmacokinetics in peritoneal dialysis patients after intravenous and intraperitoneal administration.

Secondary endpoint is to evaluate patients for any adverse effects potentially associated with intraperitoneal administration of dalbavancin.

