#### C. Study Design and Research Methods

This study is an open label, cross-over study, evaluating the plasma and peritoneal fluid pharmacokinetics of dalbavancin after either intravenous or intraperitoneal administration. The

patients will be randomly assigned to receive dalbavancin either intravenously or intraperitoneally on study visit 1. The patients will receive the alternate administration technique following the washout period at visit 4. Patients will be administered dalbavancin either intravenously or intraperitoneally on study day 0. Pharmacokinetic analysis will be conducted on days 0, 7, and 14. Following the wash out period of 45 days or greater, the same 10 patients will cross-over and then be administered dalbavancin via the alternate administration technique received in visit 1 on study day 0. Pharmacokinetic analysis will be conducted again on days 0, 7, and 14. (see Appendix 1)

*Sample Size:*

Ten (n=10) patients will be evaluated in this pharmacokinetic evaluation. Since this is a descriptive pharmacokinetic study a sample size calculation was not performed

*Plasma and peritoneal fluid sampling:*

Dalbavancin will be administered on study day 0. On the intravenous administration day dalbavancin will be administered as a 30-minute IV infusion. On the intraperitoneal administration day, dalbavancin will be administered in the peritoneal dialysis fluid with a 6 hour dwell time. On day 0, patients will undergo plasma and peritoneal fluid pharmacokinetic sampling for determination of dalbavancin concentrations at time zero, 1 hour, 2 hours, 3 hours, 4 hours, 6 hours, at time of volume exchange. Patients will be given a specimen collection cup and asked to collect ~30 ml of peritoneal dialysate following scheduled nocturnal dwell approximately 24 hours following the administration of dalbavancin administration. Patients will report for a single PK measurement on study days 7 and 14. (18 total plasma and 18 total peritoneal fluid samples per patient). Blood samples will be drawn from a peripherally inserted intravenous catheter. Peritoneal fluid samples will be drawn from the already placed peritoneal dialysis catheter. Blood samples will be immediately centrifuged at 3000g and plasma and peritoneal fluid samples will be stored at -80°C until analysis.

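### Peritoneal clearance and fraction absorbed are dimensionally wrong as written, and the dialysate AUC has no rule for the drain and refill after the intraperitoneal dwell

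*Combined protocol and SAP*

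**What the plan says.** Peritoneal fluid pharmacokinetics by both routes is a primary endpoint. Section IV.A sets out to "determine dalbavancin peritoneal fluid pharmacokinetics in peritoneal dialysis patients after intravenous and intraperitoneal administration".

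Section IV.F (Pharmacokinetic analysis) introduces its list with "The following PK parameters will be calculated for plasma and dialysate samples". The entries that matter here are:

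- Peritoneal clearance: "dalbavancin concentration in spent dialysate/AUC of peritoneal fluid". Non-dialysis clearance is then plasma clearance minus this quantity.
- Fraction of IP dose absorbed: dose minus the drug concentration left in the dialysate at the end of the dwell, divided by dose.
- AUC0-∞ by the linear trapezoid, and AUC0-12 likewise: "hours – linear trapezoidal method".
- The plasma/dialysate ratio, at each time point and as a ratio of AUCs.

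Section IV.C says that on the IP day "dalbavancin will be administered in the peritoneal dialysis fluid with a 6 hour dwell time". Day 0 samples are at 0, 1, 2, 3 and 4 hours, then "6 hours, at time of volume exchange". A dialysate sample is collected at home at about 24 h. After that, "Patients will report for a single PK measurement on study days 7 and 14". The stated total is "18 total plasma and 18 total peritoneal fluid samples per patient".

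No section plans to record drained volume, describes how AUC is handled at an exchange, or lists a 12 h sample.

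**The concern.** Two separate problems affect the primary peritoneal endpoint.

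**Formulas.** A clearance is an amount removed divided by the exposure that drives the removal. The plan's peritoneal clearance has a concentration on top and the exposure of the same fluid underneath. It says nothing about how much drug crosses from plasma to dialysate, and it makes non-dialysis clearance undefined. The fraction absorbed omits the volume that would turn a concentration into an amount. If the F in the plan's systemic clearance, (F × Dose)/AUC, is this fraction, the error carries into IP systemic clearance. If drained volume is not recorded, neither quantity can be recovered later from measured data.

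**AUC across an exchange.** Draining the dosed dwell and refilling makes the dialysate concentration drop abruptly. A straight line from the end of that dwell to a later sample counts area under fluid that has left the cavity. The drop comes from draining the fluid that carried the dose, so the IV day has no matching error that would cancel it. It reaches the plasma/dialysate AUC ratio and any between-route comparison of dialysate AUC.

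**Working it through.** The plan gives no numerical value for any of these quantities, so there is no figure of its own to reproduce.

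**1. Units of peritoneal clearance.** (mg/L) ÷ (mg·h/L) = 1/h. Plasma clearance is in L/h, so the planned subtraction is undefined.

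The quotient also carries no information on transfer. Multiply every dialysate concentration by any constant and numerator and denominator scale together, leaving it unchanged. A flat 6 h dwell gives C/(6C) = 0.167 per h for any drug. For the IP dosing dwell, with first-order loss of a fraction f over 6 h and ka = −ln(1−f)/6, it equals (1−f)·ka/f. That is 0.139 per h at f = 0.3 and 0.043 per h at f = 0.9.

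**2. Fraction absorbed.** Dose 1500 mg (section IV.D). Assume a 2 L volume and f = 0.5.

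- Starting concentration: 1500/2 = 750 mg/L. At 6 h: 375 mg/L.
- As written: (1500 − 375)/1500 = 75%.
- With volume: (1500 − 375 × 2)/1500 = 50%.

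**3. IP dialysate AUC0-12.** From the plan: 1500 mg, a 6 h dwell, the sampling times and the linear trapezoid. Assumed: 2 L fill, f from 0.3 to 0.9, 10% residual after drain, and a 24 h level (C24) of 5 to 50 mg/L. After the drain the concentration is held at the larger of 0.1 × C6 and C24 until 12 h.

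Example with f = 0.5 and C24 = 5 mg/L, so ka = 0.1155 per h and C6 = 375 mg/L:

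- True area 0–6 h: (750 − 375)/0.1155 = 3246. True area 6–12 h: 6 × 37.5 = 225. Total 3471 mg·h/L.
- Trapezoid 0–6 h: 3252, an error of +0.2%.
- *Exchange sample is the 6 h sample or first-dwell fluid.* The line runs from 375 at 6 h to 5 at 24 h and reads 251.7 at 12 h. Area 6–12 h: 6 × (375 + 251.7)/2 = 1880. Total 5132, or +48%.
- *Exchange sample is second-dwell fluid at 8 h.* Area 6–8 h: 2 × (375 + 37.5)/2 = 412.5. The line reads 29.4 at 12 h, so area 8–12 h is 4 × (37.5 + 29.4)/2 = 133.8. Total 3799, or +9%.

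Error in AUC0-12 over the range:

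| f | second-dwell sample, C24 = 5 | second-dwell sample, C24 = 50 | first-dwell or same sample, C24 = 5 | first-dwell or same sample, C24 = 50 |
|---|---|---|---|---|
| 0.3 | +11.0% | +11.5% | +56.5% | +57.6% |
| 0.5 | +9.4% | +9.3% | +47.9% | +46.0% |
| 0.7 | +7.6% | +6.5% | +36.7% | +30.5% |
| 0.9 | +5.3% | +2.7% | +20.2% | +7.5% |

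A second model gave +3% to +6% with a refill sample 1 h after the drain, and +19% to +63% with end-of-dwell fluid. It used 2.0–2.5 L fills, 5–15% residual, exchanges every 6 h and low back-diffusion from plasma. Integrating only from 0 to the drain errs by +0.1% to +1.7%.

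If plasma AUC were exact, the plasma/dialysate AUC ratio would be too low by 3% to 11% (1/1.03 to 1/1.12) on the first reading, and by 7% to 37% (1/1.08 to 1/1.58) on the second.

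**4. Which sample is it?** Counting the listed samples over two periods:

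- Exchange sample separate from 6 h: plasma (6 + 1 + 2) × 2 = 18; peritoneal (6 + 1 + 1 + 2) × 2 = 20.
- Exchange sample is the 6 h sample: plasma (6 + 2) × 2 = 16; peritoneal (6 + 1 + 2) × 2 = 18.

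Neither gives 18 of each unless the home-collected sample is left out of the count. Section IV.D ends day 0 at a second volume exchange, which favours a separate sample. It does not say whether that fluid is taken before drain or after refill.

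**The case against.** The strongest defence is that the trapezoid is not the whole analysis. Section IV.F opens with compartmental modelling of plasma and peritoneal fluid data and ends with a mixed-effects model. Both could treat an exchange as an event. However, the plan does not say they will, and it states that AUC is trapezoidal.

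It is also fair that the parameter list cannot apply item by item to both fluids; systemic clearance, for example, belongs to plasma only. A dialysate AUC0-∞ is therefore an inference. Some dialysate AUC is still required, because the plan forms the plasma/dialysate AUC ratio.

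The clearance formula might be shorthand for amount recovered. But no volume is planned to be recorded, and an amount over peritoneal-fluid AUC would still not be a clearance from plasma.

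Stronger readings are tempting, and the documents do not support them:

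- *That IP dialysate AUC will be inflated by half.* The larger errors need the exchange sample to be first-dwell fluid. The text leans towards a separate sample, and every percentage rests on assumed kinetics.
- *That the detectable AUC difference of 1527 mg·hr/L in section IV.F is distorted by a known amount.* The plan does not say which AUC or which fluid that figure concerns.
- *That peritoneal target attainment is wrong.* The simulation text compares MICs with plasma concentrations, although its stated aim mentions both fluids. The consequence holds only if a dialysate AUC0-12 is used.
- *That both routes share a 6 h dwell.* The 6 h figure is given for the IP day only.

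**Conclusion.** Two parts are certain from the text alone. Peritoneal clearance and fraction absorbed are wrong as written, and non-dialysis clearance falls with the first. The dialysate AUC has no rule for the drain and refill.

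The size of the AUC error is conditional. IP dialysate AUC0-12 *can* be overstated, by about +3% to +12% with a separate second-dwell sample at about 8 h, or about +8% to +58% with the 6 h sample or drained first-dwell fluid. Both ranges assume a 2 L fill, 30–90% absorbed, 10% residual and 5–50 mg/L at 24 h. The direction was the same in every scenario run.

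A dialysate AUC0-∞, if computed, has no clear meaning: days 7 and 14 each contribute one sample at no stated time into a dwell. This should be fixed before data collection, since volumes and times not recorded cannot be recovered.

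**What to change.** 1. Record fill times, drain times and drained volumes.
2. Define peritoneal clearance as (concentration × drained volume) / plasma AUC over the same interval, taken from the IV-day dwell. Do not take it from the IP dosing dwell, whose drain holds unabsorbed dose. State that IP-period peritoneal clearance is dropped or model-based, because no plasma sample is paired with the 24 h dialysate sample.
3. Define fraction absorbed as (dose − concentration × drained volume)/dose.
4. Compute dialysate AUC from 0 to the drain of the dosing-day dwell, which is 6 h on the IP day. State the IV-day dwell length, and use the same interval if it is also 6 h. Form the plasma/dialysate AUC ratio over that interval.
5. Build any 0–12 h dialysate value dwell by dwell. Do not report dialysate AUC0-∞. Report 24 h, day 7 and day 14 as concentrations at a recorded dwell time, with the dialysate/plasma ratio on days 7 and 14, where plasma is paired.
6. If compartmental or mixed-effects models are fitted to dialysate, code each exchange as a drain-and-refill event.
7. State whether the exchange sample is separate from the 6 h sample and whether it is taken before drain or after refill. Reconcile the 20 listed peritoneal samples with the stated 18.

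The cost is wording, extra recording of times and volumes, and somewhat more analysis, with no new samples. Two limitations remain and should be reported: any 0–12 h dialysate value stays approximate, and the IP period yields no directly measured peritoneal clearance.

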### **II. Background and Significance:**

Every year in the United States approximately 110,000-115,000 patients are newly diagnosed with end-stage renal disease (ESRD) and begin treatment with renal replacement therapy. Nearly 10,000 of these patients are started on peritoneal dialysis (PD). The use of home dialysis has increased significantly (35% increase) in the last decade, with 95% of home dialysis patients undergoing PD. Infectious peritonitis is a leading major morbidity associated with PD, and it accounts for approximately 18% of infection-related mortality in PD patients. Severe or prolonged peritonitis can lead to peritoneal membrane failure, ultimately causing technical failure of PD and requiring transition to traditional hemodialysis methodologies. Rapid and effective treatment of peritonitis is required to reduce inflammation and preserve peritoneal membrane function. The current standard of care involves empiric antibiotics covering gram positive organisms as staphylococcus aureus, coagulase negative staphylococcus and enterococcus are common infecting pathogens. Vancomycin is commonly employed at most institutions as there is a risk of MRSA infections in this patient population. Addition of a second drug for gram negative bacteria coverage is recommended until culture and sensitivity results are available. Intravenous or intraperitoneal administration of antibiotics can be utilized; however, guidelines recommend the intraperitoneal administration of antibiotics with a dwell time of at least 6 hours because it provides instant, high, and sustained concentrations of the antibiotic in the peritoneal fluid. Although vancomycin covers the majority of gram positive organisms that cause peritonitis, its use can be cumbersome in PD patients. Plasma vancomycin drug concentration monitoring must occur to evaluate for vancomycin accumulation. Additionally, vancomycin must be re-administered every 3-5 days in order to maintain steady-state trough concentrations around 15 mcg/ml. Similarly to vancomycin, dalbavancin interferes with cell wall synthesis. This is done through binding of the D-alanyl-D-alanine terminus of the cell wall peptidoglycan. Dalbavancin has been shown to rapidly reach therapeutic systemic concentrations and to have an extended half-life of ~8.5 days. Dalbavancin has been shown safe and effective with a treatment doses of 1500 mg once or 1000 mg followed by a 500 mg dose on day 7. Dalbavancin pharmacokinetics were evaluated in patients who had hepatic or renal impairment. This study showed compared to healthy subjects dalbavancin exposure was not increased in mild renal impairment, exposure was ~50% higher in moderate renal impairment, 100% higher in severe renal impairment, and not significantly different in end stage renal disease

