#### B. Description of Population to be Enrolled:

##### Inclusion criteria:

- Age  $\geq 18$  to  $\leq 89$  years of age
- Actively receiving chronic peritoneal dialysis (receiving peritoneal dialysis treatments  $\geq 3$  times per week for  $\geq 3$  months)
- Ability and willingness to provide written informed consent before the first trial ready activity

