**D. Description, Risks and Justification of Procedures and Data Collection Tools:**

**Enrollment and Screening:** Study subjects will be contacted an enrolled through [name] clinic. Initial contact will be made by phone prior to a clinic appointment to discuss initial interest of the patient. Further information and enrollment will take place at a clinic visit or time of the patients choosing. Enrollment will take place in a private room at [name] clinic. Initial baseline and demographic information will be gathered for enrolled patients at the time of enrollment. Safety labs (comprehensive metabolic panel and urine pregnancy test for women of childbearing potential) will be drawn or performed at [name] clinic and will coincide with a scheduled clinic visit closest to study protocol initiation. The comprehensive metabolic panel will be drawn to evaluate Child-Pugh score if there is no comprehensive metabolic panel within the medical record within 30 days of protocol initiation.

**Visit 1 and 4:** (~8 hours): On visits 1 and 4 the patients will undergo intensive PK sampling. Inclusion and exclusion criteria will be reviewed with the patient at each visit prior to initiation of the protocol. Subjects will be admitted to the CTRC in the morning and a "saline-lock" will be placed. The dalbavancin preparations will be prepared and managed by [name] or [name] who are both clinical pharmacists with training in sterile drug preparation. The dalbavancin 1500 mg will either be administered, by CTRC nursing staff, intravenously (as randomly assigned) or into the intraperitoneal space (as randomly assigned) using the patient's existing peritoneal dialysis catheter with the patients currently prescribed dialysate. Following the blood and peritoneal fluid collection at the second dialysis volume exchange, the subjects will be discharged and asked to return at a scheduled time on day 7. Patients will also be given a specimen collection up with instructions to collect approximately 30 ml of peritoneal dialysate following their evening nocturnal dwell. The collected dialysate will be returned to the investigators.

**Visit 2, 3, 5, and 6:** (~60 minutes): A "saline-lock" will be placed and a single blood and peritoneal fluid sample will be collected at each of these visits. All blood and peritoneal fluid draws will be

completed at the outpatient CTTC. The patient will be discharged and follow up visits will be scheduled for day 14 or next intensive PK sampling visit.

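### Fraction of IP dose absorbed and peritoneal clearance are written with a concentration where an amount is needed, peritoneal clearance also has the wrong denominator, and no drained volume is recorded

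*Combined protocol and SAP*

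**What the plan says.** Section IV.F, Pharmacokinetic analysis, lists the parameters to be derived. Three matter here.

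- Fraction absorbed: "Fraction of intraperitoneal (IP) dose absorbed [(Dose – drug concentration remaining in dialysate at end of" the dwell, all over Dose. There is no volume term.
- Peritoneal clearance: "Clearance peritoneal – dalbavancin concentration in spent dialysate/AUC of peritoneal fluid". The interval of that AUC is not given; the AUCs named elsewhere in the list are 0 to infinity and 0 to 12 h.
- Non-dialysis clearance: "Cl = Cl_{plasma} - Cl_{peritoneal", that is, plasma clearance minus the term above.

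The dose is 1500 mg (IV.D, Visit 1 and 4). AUC is expressed in mg·hr/L (IV.F, Statistical comparisons), so concentrations are in mg/L.

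On sampling, IV.C takes day-0 samples up to "3 hours, 4 hours, 6 hours, at time of volume exchange", and patients are then "asked to collect ~30 ml of peritoneal dialysate following scheduled nocturnal dwell". IV.D sets 4 mL of peritoneal fluid per sample and has patients leave "Following the blood and peritoneal fluid collection at the second dialysis volume exchange". The dialysate is whatever each patient is currently prescribed. These sections and the Appendix 2 schedule plan samples for concentration. None asks for instilled or drained volume to be recorded. The content of Appendix 1 is not shown in the text available.

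**The concern.** A dose is an amount and a dialysate concentration is not, so their difference has no meaning until the concentration is multiplied by a volume. A concentration divided by an AUC is a rate (1/h), not a clearance (L/h). Non-dialysis clearance then subtracts a quantity in 1/h from one in L/h.

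Fraction absorbed describes how much of an intraperitoneal dose enters the body, and peritoneal clearance describes how much drug the dialysis removes. If the formulas were programmed as printed, the first would be biased upward for any drain above 1 L, and the second would not measure transfer across the membrane. The wording can be corrected at analysis, but the volume has to be available, and nothing in the visible text provides for collecting it.

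**Working it through.** The plan gives no figure of its own for these parameters, so there is none to reproduce. Drained volume, extent of transfer and the IV-day dwell length are not in the documents and are assumed below. The 6 h dwell is stated for the IP day only.

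**1. Fraction absorbed.** Let f be the true fraction absorbed and V the drained volume in litres. The amount left is Dose × (1 − f), so the drain concentration is C = Dose × (1 − f)/V. Put into the written formula:

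(Dose − C)/Dose = 1 − (1 − f)/V

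This equals f only when V = 1.

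| Assumed drain | True 0% | True 50% | True 80% |
|---|---|---|---|
| 1.5 L | 0.333 | 0.667 | 0.867 |
| 2 L | 0.50 | 0.75 | 0.90 |
| 3 L | 0.667 | 0.833 | 0.933 |

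If amount was meant and a nominal fill of 2.0 L stands in for the unrecorded drain, the estimate is 1 − (1 − f) × 2.0/V. For a true 50%:

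- 2.2 L drained: 1 − 0.5 × 2.0/2.2 = 0.545 (as written: 0.773)
- 2.4 L drained: 1 − 0.5 × 2.0/2.4 = 0.583 (as written: 0.792)

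Including a volume removes most of the error; using the drained volume removes the rest.

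**2. Peritoneal clearance, units.** (mg/L)/(mg·h/L) = 1/h.

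**3. Peritoneal clearance, denominator.** Take an IV-period dwell of T = 6 h with plasma concentration Cp roughly constant. Let dialysate rise from zero to a fraction r of Cp by the end of the dwell, with rate k = −ln(1 − r)/6. Then:

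- end-of-dwell dialysate concentration = r × Cp
- peritoneal-fluid AUC over the dwell = Cp × (6 − r/k)
- written value = r/(6 − r/k); Cp cancels
- amount over plasma AUC = r × V/6

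| r | k (per h) | Written value (per h) | Amount over peritoneal-fluid AUC, 2 L (L/h) | Amount over plasma AUC, 2 L (L/h) |
|---|---|---|---|---|
| 2% | 0.00337 | 0.332 | 0.664 | 0.0067 |
| 5% | 0.00855 | 0.331 | 0.661 | 0.0167 |
| 10% | 0.01756 | 0.328 | 0.655 | 0.0333 |

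Transfer rises five-fold down the table. The last column follows it. The written value, and the version with amount in the numerator, move by about 1%. At low transfer the written value is close to 2/T, which is a function of dwell length.

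**4. AUC interval.** With AUC 0–12 h over two equal 6 h dwells, the written value halves, to about 0.166 per h at 2% transfer. With AUC to infinity, assuming continuous equal dwells whose mean dialysate concentration is half the end value, it is about 2 × Kel. The Background describes dalbavancin as having been shown "to have an extended half-life of ~8.5 days", so Kel = 0.693/(8.5 × 24) = 0.0034 per h, and the value is about 0.007 per h. The unstated interval therefore changes the result greatly, and on none of these readings does it measure transfer.

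**5. Non-dialysis clearance.** Systemic clearance, F × Dose/AUC, has units mg/(mg·h/L) = L/h and is dimensionally sound. The fault enters through the peritoneal term: L/h minus 1/h is undefined.

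**The case against.** The best defence is that concentration is loose wording. Drug remaining in the dialysate, set against Dose, reads naturally as an amount, and few analysts would subtract mg/L from mg. For fraction absorbed this largely stands: with a volume supplied the formula is correct, and even a nominal fill leaves only a modest bias. A volume must still come from somewhere, and none is planned in the visible text. For peritoneal clearance the defence fails, because amount over peritoneal-fluid AUC has the right units but does not respond to transfer.

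It is also fair to say that the study is described as descriptive, that its hypothesis concerns adequate concentrations over two weeks, and that the quantities bearing on that hypothesis do not use these formulas. This stands, and it limits the severity.

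Three stronger readings are tempting, and the documents do not support them.

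- A reader might infer that the written clearance builds in a two-fold difference between routes. That appears (ratios of about 2.01 to 2.07 at 2 to 10% transfer) only with a 0–6 h AUC, which the plan does not name for this term. With the named 0–12 h AUC over two equal dwells the ratio is about 1.01 to 1.04. The plan also does not say that peritoneal clearance will be compared between routes; it names AUC alone for the detectable difference.
- A reader might infer that non-dialysis clearance must come out negative. That needs an assumed volume of distribution, an assumed AUC interval, and a subtraction of unlike units. The supportable statement is that it is not valid as defined.
- A reader might infer that a named primary endpoint is invalid. Section IV.A names plasma and peritoneal-fluid pharmacokinetics as primary but lists no individual parameters.

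Nor do the documents show that drained volume will be unavailable: case report forms and dialysis records are not part of them. They show only that no visible section asks for it.

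**Conclusion.** Wrong as written, and should be fixed. Both formulas put a concentration where an amount is required, and this needs no assumption to establish. The peritoneal-clearance denominator is a separate error that survives the generous reading, and its AUC interval is unspecified. Non-dialysis clearance is not valid because it depends on that term.

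The sizes rest on assumptions. The reporting of 0, 50 and 80% absorption as 50, 75 and 90% assumes a 2 L drain and literal use of the formula; the 0.545 and 0.583 for a true 0.50 assume a nominal 2.0 L fill with 2.2 and 2.4 L drained. The near-constant 0.33 per h assumes a 6 h IV-period dwell, steady plasma concentration and 2 to 10% transfer.

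Measured concentrations, the AUCs, plasma/dialysate ratios, target attainment and the paired AUC comparison are not affected.

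**What to change.** 1. Define fraction absorbed during the dosing dwell as (Dose − C_drain × V_drain)/Dose.
2. Define peritoneal clearance as (C_drain × V_drain)/plasma AUC over the same dwell, from IV-period dwells. Exclude the IP dosing dwell, because its drain contains unabsorbed dose.
3. Compute non-dialysis clearance in L/h from the IV period with that term, stating the assumption that the sampled dwell represents the patient's other dwells, or drop it.
4. Record instilled volume, drained volume, and dwell start and end times at the exchange that ends the day-0 dwell in each period and at the exchange sampled at about 24 h.

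The cost is SAP wording and one data item per sampled exchange. Reported fraction absorbed will be lower than the printed formula gives for drains above 1 L, and peritoneal and non-dialysis clearance will be available for the IV period only.
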